4. PATIENT SELECTION CRITERIA

4.1. Overview

This clinical study can fulfill its objectives only if appropriate patients are enrolled. The following eligibility criteria are designed to select patients for whom study participation is considered appropriate. All relevant medical and non-medical conditions should be taken into consideration when deciding whether this protocol is suitable for a particular patient. Eligibility criteria may not be waived and conformance to the eligibility criteria is subject to review in the case of a Good Clinical Practice (GCP) or a regulatory authority audit. Any questions regarding a patient's eligibility should be discussed with the PTC Therapeutics medical monitor prior to enrollment.

4.2. Inclusion Criteria

Patients must meet all of the following conditions to be eligible for enrollment into the study:

1. Completion of study treatment in the previous Phase 3, double-blind study protocol (Protocol PTC124-GD-020-DMD).
2. Evidence of signed and dated informed consent/assent document(s) indicating that the patient (and/or his parent/legal guardian) has been informed of all pertinent aspects of the trial.
Note: If the study candidate is considered a child under local regulation, a parent or legal guardian must provide written consent prior to initiation of study screening procedures and the study candidate may be required to provide written assent. The rules of the responsible Institutional Review Board/Independent Ethic Committee (IRB/IEC) regarding whether one or both parents must provide consent and the appropriate ages for obtaining consent and assent from the patient should be followed.

3. In patients who are sexually active, willingness to abstain from sexual intercourse or employ a barrier or medical method of contraception during the study drug administration and 6-week follow-up period.
4. Willingness and ability to comply with scheduled visits, ataluren administration plan, study procedures, laboratory tests, and study restrictions.

4.3. Exclusion Criteria

Prior to treatment with study drug, it will be confirmed that the patient meets none of the following conditions:

1. Known hypersensitivity to any of the ingredients or excipients of the study drug (Litesse® Ultra™ [refined polydextrose], polyethylene glycol 3350, Lutrol® micro F127 [poloxamer 407], mannitol 25C, crospovidone XL10, hydroxyethyl cellulose, vanilla, Cab-O-Sil® M5P [colloidal silica], magnesium stearate).
2. Ongoing participation in any other therapeutic clinical trial.
3. Prior or ongoing medical condition (eg, concomitant illness, psychiatric condition, behavioral disorder, alcoholism, drug abuse), medical history, physical findings, ECG findings, or laboratory abnormality that, in the investigator's opinion, could adversely affect the safety of the patient, makes it unlikely that the course of treatment or follow-up would be completed, or could impair the assessment of study results.

5. ENROLLMENT PROCEDURES

5.1. Source and Number of Patients

Patients for this Phase 3 extension study are derived only from those who completed blinded study drug in the Phase 3 study (PTC124-GD-020-DMD).

5.2. Screening and Study Drug Allocation

The investigator must inform each prospective patient of the nature of the study, explain the potential risks, and obtain written informed consent/assent from the patient and/or the parent/legal guardian prior to performing any study related screening procedures.

The patient number used in the prior Phase 3 study (Protocol Number PTC124-GD-020-DMD) shall be retained for use in this study. This patient number must be used for patient identification on all study-related documents (case report forms [CRFs], clinic notes, laboratory samples, etc).

The user will need to supply the Interactive Voice Response/Interactive Web Response (IVR/IWR) system with the information required by the system (eg, site number, patient number).

6. STUDY DRUG ADMINISTRATION

6.1. Investigational Product

6.1.1. Ataluren (PTC124)

Ataluren will be provided as a white to off-white powder for oral suspension. The drug has been manufactured under cGMP conditions. The formulation includes matrix and suspending agents, surfactants, and various excipients that aid in the manufacturing process. The powder for oral suspension are packaged in aluminum-foil, child-resistant sachets (packets) and supplied in dose strengths containing 125, 250, or 1000 mg of the active drug substance. For administration, the powder in the sachet may be mixed with water, milk (skim, 1% fat, 2% fat, whole milk, chocolate milk, or lactose-free milk), or in semi-solid food (yogurt, pudding, or applesauce).

6.1.2. Drug Kits

Drug kits will be provided, each of which contains 90 sachets of one of the dose strengths (125, 250, or 1000 mg.).

6.1.3. Study Drug Packaging and Labeling

Sachets and cartons will be color coded to indicate dosage strength (125 mg – yellow, 250 mg – pink, 1000 mg – blue).

Labels will be provided in appropriate languages as required by each country in which the study is conducted. The content of the labeling will be in accordance with local regulatory specifications and requirements.

6.1.4. Study Drug Dispensing

Dosing of ataluren will be based on milligrams of drug per kilogram of patient body weight at Screening/Baseline (Visit 1) and will be adjusted to allow for dosing with the available sachet dose strengths. The sachet dosage strengths and number of sachets to be taken per dose will be provided by the IVR/IWR system.

The clinic staff (eg, pharmacist or other qualified person) will be responsible for dispensing study drug according to the IVR/IWR system directions. Sufficient study drug will be provided for each study period at the beginning of the period.

Because of potential changes in patient body weight over time, weight-based dose adjustments will occur every 6 months. Depending upon the magnitude of change in patient body weight since baseline, the number and type of sachets to be used by the patient may remain the same or may be adjusted.

6.1.5. Return of Study Drug

Patients should return all remaining study drug (all unused sachets) to the study site at the end of each 12-week treatment period for inventory. The Study Drug Administration Record will serve as the source document for drug supply to the patients and will document the return of any unused drug for compliance assessments.

6.1.6. Storage and Stability

Kits containing sachets of study drug will be shipped and stored at room temperature (~15 to 30°C). The available stability data from representative samples support the use of the drug product for 48 months when stored at room temperature. The stability of the clinical study samples or representative samples will be monitored to support the clinical study.

6.1.7. Study Drug Accountability

Study personnel must ensure that all study drug supplies are temperature monitored and kept in a secure locked area with access limited to authorized personnel. This study product must not be used outside the context of this protocol. Under no circumstances should the investigator or site personnel supply study product to other investigators or clinics, or allow the supplies to be used other than as directed by this protocol.

The investigator and/or the responsible site personnel must maintain accurate records of the receipt of all study drug shipped by PTC Therapeutics or its designee, including, but not limited to, the date received, lot number, amount received, and the disposition of all study drug. Current reconciliation and dispensing records must also be maintained that include the date and amount of drug dispensed, and patient's assigned study number.

Depending upon the decision of PTC Therapeutics, unused clinical supplies must be destroyed or must be returned to PTC Therapeutics or its designee after the study is completed.

Accountability must be verified by the site monitor prior to return or destruction. Records documenting the date of study drug destruction or shipping, relevant sachet numbers, and amount destroyed or shipped should be kept in the investigator site study file.

6.1.8. Overdose Precautions

For any patient experiencing an overdose (administration of a study drug dose >4 times the highest intended total daily dose level for this protocol [>160 mg/kg/day]), observation for any symptomatic side effects should be instituted, and vital signs and biochemical and hematological parameters should be followed closely (consistent with the protocol or more frequently, as needed). Appropriate supportive management to mitigate adverse effects should be initiated. Pending the acquisition of sufficient human experience with the drug, use of gastric lavage or induction of emesis is not specifically recommended nor contraindicated.

The PTC Therapeutics medical monitor must be contacted if an overdose occurs. Under applicable regulations, overdosing may be considered an SAE and should be reported accordingly (see [Sections 8.1.1](#) and [8.1.2](#)).

6.1.9. Inadvertent Exposure and Spill Precautions

Reference can be made to the Ataluren Investigator Brochure for current information on inadvertent exposures and spill precautions.

6.2. Study Drug Treatment

6.2.1. Duration of Treatment

In this study, treatment will comprise continuous daily treatment with ataluren for up to 144 weeks (~3 years). This study may be further extended by amendment until either ataluren becomes commercially available or the clinical development of ataluren in DMD is discontinued.

6.2.2. Schedule of Administration

As noted in Table 1, 3 doses should be taken per day – the 1st dose in the morning, the 2nd dose during the middle of the day (mid-day), and the 3rd dose in the evening. Ideally each dose should be taken within ~30 minutes after a meal (eg, ~7:00 AM after breakfast, ~1:00 PM after lunch, and ~7:00 PM after dinner). Intervals for dosing should be ~6 hours (± 1 hour) between morning and mid-day doses, ~6 hours (± 1 hour) between mid-day and evening doses, and ~12 hours (± 1 hour) between evening doses and the morning dose on the next day. While it is realized that variations in dosing schedule may occur in the outpatient setting, the prescribed regimen (including dosing intervals and the relationship of dosing to meals) should be followed closely on the day preceding PK sample collection in the clinic.

Table 1. Suggested Daily Dosing Schedule

Dose Designation	Preceding Meal	Example Dosing Times ^a
Morning	Breakfast	~7:00 AM – 0700 hours (± 1 hour)
		↑ ~6 hours ↓
Mid-day	Lunch	~1:00 PM – 1300 hours (± 1 hour)
		↑ ~6 hours ↓
Evening	Dinner	~7:00 PM – 1900 hours (± 1 hour)
		↑ ~12 hours ↓
Next Day Morning	Breakfast	7:00 AM – 0700 hours (± 1 hour)

- a Dosing times are examples and may be varied to suit each patient's schedule. However, the time between morning and midday doses and between midday and evening doses should be maintained at ~6 hour intervals, while the time between the evening and next morning dose should be maintained at an ~12 hour interval.

6.2.3. Instructions for Delays in Dosing

If a patient experiences a delay in the administration of study drug of ≤ 1 hour, the planned dose should be taken with no changes to the subsequent dose schedules. For a patient who has a delay of >1 hour but ≤ 4 hours, the planned dose should be taken; however, all future doses for that day should be shifted later by an approximately corresponding amount. For a patient who has a delay in administration of study drug of >4 hours, the dose should not be taken. Study drug administration may continue but the missed dose should not be made up and the planned timing of subsequent study drug dosing should not be altered.

6.2.4. Study Drug Preparation and Storage

Study drug sachets should be stored and monitored at room temperature, away from the reach of children until time of reconstitution. The powder in the sachet may be mixed with water, milk (skim, 1% fat, 2% fat, whole milk, chocolate milk, or lactose free milk) or in semi-solid food (yogurt, pudding, or applesauce). The number of sachets to be taken for a dose should be separated from the total number of sachets dispensed for the patient. The full contents of the sachets should be mixed with at least 30 mL (1 ounce) of liquid, or 3 tablespoons of semi-solid food. The prepared dose should be mixed well before administration. The amount of the liquid or semi-solid food can be increased based on patient preference.

The clinic staff will instruct each patient or parent/caregiver on the specific number of sachets to be taken from each kit at each dose and will provide detailed oral directions regarding drug preparation. In addition, detailed written drug mixing and dosing instructions will be provided to the patient or parent/caregiver when drug supplies are dispensed. The clinic staff should attempt to follow up with the patient/caregiver regarding the drug preparation and dosing procedures within an appropriate interval (eg, 1 week) after initiation of study treatment.

6.3. Safety Monitoring and Study Drug Dose Interruption/Modification

6.3.1. Laboratory Abnormalities and Adverse Events Requiring Evaluation and Potential Drug Interruption/Modification

Patients must be monitored closely for adverse events or laboratory abnormalities during the course of the study.

For adverse events or laboratory abnormalities, the investigator will use judgment in determining whether the event or abnormality is clinically significant, whether diagnostic evaluation is warranted, and whether potential interruption of study drug treatment is appropriate. In general, life-threatening (Grade 4) or severe (Grade 3) adverse events or laboratory abnormalities should be considered clinically significant, although recurrent or persistent moderate events (Grade 2) may also be considered clinically significant in certain circumstances. Reference should be made to the Common Terminology Criteria for Adverse Events (CTCAE), Version 3.0 (see http://ctep.cancer.gov/protocolDevelopment/electronic_applications/docs/ctcae3.pdf) for grading the severity of adverse events and laboratory abnormalities.

Table 2 provides information on actions to be taken in the event that abnormalities are noted in specified laboratory parameters. Thresholds are provided for interrupting study drug immediately, for interrupting study drug after confirmation of a value beyond the threshold, or for continuing study drug while evaluating for potential drug-related toxicity. For adverse events or laboratory abnormalities not listed in **Table 2**, the investigator should use his/her judgment in determining whether the event or abnormality is clinically significant, whether diagnostic evaluation is warranted, and whether potential interruption of study drug is appropriate.

Table 2. Safety Monitoring Parameters and Actions To Be Taken

Organ System and Laboratory Parameter	Stop Study Drug Immediately, Confirm Abnormal Value, and Then Start Work-Up	Stop Study Drug After Confirming ^a Abnormal Value, and Then Start Work-Up	Continue Study Drug, Confirm Abnormal Value, and then Start Work-Up ^a
Hepatic			
Serum total bilirubin	≥Grade 3 (≥3.0 x ULN)	Grade 2 (1.5 – 3.0 x ULN)	---
Serum GGT	≥Grade 3 (≥5.0 x ULN)	Grade 2 (>2.5 – 5.0 x ULN)	---
Serum ALT			↑ of > 150 U/L with stable or ↓ CK
Renal			
Serum cystatin C	>2.00 mg/L	>1.33 – 2.00 mg/L	---
Serum creatinine	≥ Grade 2 (≥1.5 x ULN for age)	Grade 1 (>ULN – 1.5 x ULN for age)	---
Serum BUN	≥3.0 x ULN	≥1.5 – 3.0 x ULN	---
Urine protein: urine creatinine (spot)	---	>0.40 mg:mg	---
Urine protein: urine osmolality (spot)	---	>0.30 mg/L:mOsm/kg	---
Urine blood (by dipstick)	4+ (Large)	3+ (Moderate)	2+ (Small)
Serum electrolytes	Grade 3-4	Grade 2	Grade 1
Serum Na ⁺ , high	>155 mmol/L	>150 – 155 mmol/L	---
Serum Na ⁺ , low	<130 mmol/L	---	---
Serum K ⁺ , high	>6.0 mmol/L	>5.5 – 6.0 mmol/L	---
Serum K ⁺ , low	<3.0 mmol/L	---	---
Serum Mg ²⁺ , high	>1.23 mmol/L	---	---
Serum Mg ²⁺ , low	<0.4 mmol/L	<0.5 – 0.4 mmol/L	---
Total serum Ca ²⁺ , high	>3.1 mmol/L	>2.9 – 3.1 mmol/L	---
Total serum Ca ²⁺ , low	<1.75 mmol/L	<2.0 – 1.75 mmol/L	---
Serum phosphorous	<0.6 mmol/L	<0.8 – 0.6 mmol/L	---
Serum HCO ₃ ⁻	<11 mmol/L	<16 – 11 mmol/L	---

^a Laboratory abnormalities may be confirmed immediately or at the next scheduled clinic visit based on investigator judgment. Abbreviations: ACTH = adrenocorticotropic hormone, ALT = alanine aminotransferase, BUN = blood urea nitrogen, Ca²⁺ = calcium, CK = creatine kinase, GGT = gamma glutamyl transferase, HCO₃⁻ = bicarbonate, K⁺ = potassium, Mg²⁺ = magnesium, Na⁺ = sodium, ULN = upper limit of normal

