6.3.2. Evaluation of Adverse Events or Laboratory Abnormalities

While specific monitoring, diagnostic testing, and supportive care measures must be instituted based on the clinical judgment of the investigator, investigators are encouraged to contact either the PTC Therapeutics medical monitor (or designee) to obtain guidance and to ascertain whether similar events are being seen at other investigator sites. The PTC Therapeutics medical monitor should be notified of any adverse event or laboratory abnormality that leads to dose interruption and should be apprised of ancillary laboratory or other diagnostic findings and the evolving data from any work-up of the initial abnormality. The PTC Therapeutics medical monitor may suggest review of the case with gastroenterology or nephrology consultants or with other experts (either at the site or retained by PTC Therapeutics).

Clinical evaluations for potential hepatic and renal toxicities may include the following:

- **Hepatic:** The medical history, all clinical blood values (particularly serum bilirubin, CK, GGT, AST, and ALT values), and all concomitant medications should be reviewed. Depending upon changes observed, the recommended diagnostic workup may include more

frequent monitoring or further evaluations for viral hepatitis and immune disorders; tests for cholelithiasis; or abdominal ultrasound, computed tomography (CT), magnetic resonance imaging (MRI), or other imaging methods.

- **Renal:** The medical history, baseline ultrasound data, all clinical blood and urine renal values, serum electrolytes, medications, and potential pre- or post renal conditions should be reviewed. Depending upon the changes observed, recommended diagnostic workup may include further evaluations of blood or urine; tests of glomerular filtration rate (GFR), concentrating ability, or other renal functions; CT, MRI, or other imaging methods; and/or renal biopsy.

6.3.3. Instructions for Resuming Study Drug Administration after an Interruption for Safety Concerns

In deciding whether to reinstitute study drug after a dose interruption for any clinically significant safety concern, the investigator should consider factors such as the type and severity of the adverse event or laboratory abnormality, the potential causal relationship of study drug, the patient's status in terms of dystrophinopathy or other health conditions, and the ability to monitor for recurrence of the event.

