13.2.3. Safety Monitoring

In response to the occurrence renal toxicology findings in the mouse and renal laboratory abnormalities in prior ataluren studies, a specific renal safety monitoring plan has been established in this study. In addition, thresholds for evaluation and intervention have been established for other types of adverse events or laboratory abnormalities observed in the study, including hepatic abnormalities. The intent is to protect patients, obtain a thorough assessment of any clinically relevant adverse events or laboratory abnormalities, and to offer recommendations for interruption and dose modification of study drug in response to potential safety signals. The nature of these risks and the

measures to monitor for them are to be reflected in the informed consent form.

As noted in [Section 6.3.1](#) patients must be monitored closely for adverse events or laboratory abnormalities during the course of the study. [Section 6.3.1](#) provides information on actions to be taken in the event that abnormalities are noted on specified monitoring studies. Thresholds are provided for interrupting study drug immediately, for interrupting study drug after confirmation of a value beyond the threshold, or for continuing study drug while evaluating for potential drug-related toxicity.

Renal Abnormalities

Overview

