13.2.5. Hepatic Monitoring Plan

Muscle breakdown results in ALT and AST values that are commonly 10- to 20-fold > ULN (Grade 3-4) in patients with DBMD. Consequently, it is not practical to exclude patients with high serum AST or ALT concentrations from enrollment in this study, and monitoring for hepatotoxicity must rely primarily on following patients for increases in bilirubin or GGT. Consistent with well-established guidelines [Abboud 2007] applied in this disease setting, even modest (Grade 2) alteration in bilirubin or GGT values should prompt interruption of study drug. While serum ALT or AST values cannot routinely serve as measures of hepatic injury in boys with DBMD, significant increases in ALT (>150 U/L) in conjunction with a stable or falling CK should prompt increased frequency of laboratory monitoring and possibly an evaluation for potential hepatotoxicity.

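### Protocol Table 2 footnote a puts no time limit on the test that triggers the stop-after-confirming rule, so dosing can run 70 to 90 days after a Grade 2 bilirubin or GGT value

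*Protocol*

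**What the plan says.** Protocol Table 2 (Section 6.3.1) sorts laboratory abnormalities into three actions. Bilirubin and GGT at Grade 3 or above stop drug at once. Grade 2 bilirubin (1.5 to 3.0 x ULN) and Grade 2 GGT (>2.5 to 5.0 x ULN) fall under "Stop Study Drug After Confirming". So do cystatin C >1.33 to 2.00 mg/L, creatinine above ULN up to 1.5 x ULN, BUN 1.5 to 3.0 x ULN, potassium >5.5 to 6.0 mmol/L and other renal and electrolyte values. An ALT rise of more than 150 U/L with stable or falling CK falls only under "Continue Study Drug, Confirm Abnormal Value, and then Start Work-Up".

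Footnote a is attached to the second and third columns and not to the first. It reads: "Laboratory abnormalities may be confirmed immediately or at the next scheduled clinic visit based on investigator judgment". No other section gives a limit in days for repeating these values.

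Section 13.2.5 explains that muscle breakdown raises ALT and AST in this disease, so "monitoring for hepatotoxicity must rely primarily on following patients for increases in bilirubin or GGT". It continues that "even modest (Grade 2) alteration in bilirubin or GGT values should prompt interruption of study drug". For the ALT/CK signal it says that such a rise "should prompt increased frequency of laboratory monitoring". Section 13.2.3 accepts a confirm-first step, describing thresholds "for interrupting study drug after confirmation of a value beyond the threshold". SAP Table 2 (Section 5.7.2) repeats the thresholds and the footnote, to define a summary.

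**The concern.** A stop rule is only as fast as the test that triggers it. For Grade 2 bilirubin or GGT the trigger is the repeat sample, and footnote a lets that sample be the one already due at the next routine visit. A boy whose first value crosses the threshold may then take a further full dispensing period of drug before the rule acts. The rationale in Section 13.2.5 reads as though a Grade 2 change in these two markers leads promptly to interruption.

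The same open wait applies to the renal and electrolyte rows in that column. Section 13.2.3 says the renal monitoring plan exists because of kidney findings in mice and renal laboratory abnormalities in prior ataluren studies. The protocol does set explicit time limits elsewhere: Section 6.4.2 requires creatinine and BUN within 24 to 48 hours of the first dose of IV aminoglycoside or vancomycin, and at least twice weekly after that. What is at stake is avoidable exposure in individual patients. No estimate or test is affected.

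**Working it through.** **Inputs**
- Visit interval: 12 weeks = 84 days (Protocol 1.2, Table 3).
- Visit window: ±7 days at each visit (Table 3).
- Supply per interval: 12 x 7 + 6 = 90 days, which reproduces the figure in Section 7.11. Unused sachets are returned each period (6.1.5).
- Doses per day: 3 (6.2.2).
- Report lag L: biochemistry goes to a central laboratory (7.7) and no turnaround is stated. Assumed 0 to 7 days.
- Limit R for a repeat sample, counted from the report: the plan has none. Assumed 7 days, with 3 and 14 shown.

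**Wait under footnote a**
- Gap between consecutive visits: T = 84 days; 84 − 14 = 70 to 84 + 14 = 98 with windows.
- Dosing from first to confirmatory sample at full compliance: min(T, 90) = 70 to 90 days, or 70 x 3 = 210 to 90 x 3 = 270 doses.
- Day 1 to Week 12, with a window at one end only: T = 77 to 91, so dosing is 77 to 90 days.
- Counted from when the first result is known: 70 − 7 = 63 to 90 − 0 = 90 days.
- Value first found at Week 144: 0 days, because treatment has ended. A value from an unscheduled sample has a shorter wait. Missed doses could stretch 90 days of drug over more calendar days.

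**Dosing avoided by a limit on the repeat**
- Next-visit route: new drug is dispensed at the visit, so the stop comes after min(T, 90) + L dosing days.
- Limited route: the stop comes at latest after L + R + L days.
- Difference: min(T, 90) − L − R.

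| R (days) | L = 0: min / nominal / max | L = 7: min / nominal / max |
|---|---|---|
| 3 | 67 / 81 / 87 | 60 / 74 / 80 |
| 7 | 63 / 77 / 83 | 56 / 70 / 76 |
| 14 | 56 / 70 / 76 | 49 / 63 / 69 |

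At R = 7 the saving is 56 to 83 dosing days, or 56 x 3 = 168 to 83 x 3 = 249 doses. For a value first found at Week 132 no drug is dispensed at the next visit, so L is subtracted once more: at L = 7 and R = 7 the saving is 70 − 14 − 7 = 49 to 90 − 14 − 7 = 69 days.

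**ALT/CK row**
- Table 2 has no stop for this signal. Drug continues whenever the repeat is taken, so the footnote adds 0 rule-mandated dosing days.

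**The case against.** The strongest reply is that the discretion is deliberate and harmless. Footnote a equally allows an immediate repeat, nothing in Table 2 bars earlier interruption, Section 6.3.1 requires close monitoring, and Grade 3 values stop drug at once. Section 13.2.9 describes the general intent that a Grade 2 event may be evaluated while dosing continues, and asks that the recommendations be applied flexibly. Expected frequency also looks low: Section 2.2.3 reports no bilirubin increases in Phase 1 and no clinically concerning laboratory abnormalities in the 174-boy Phase 2b study. Finally, SAP Sections 5.2 and 7 record that the sponsor is ending the study.

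Most of this stands and keeps the point small. It does not remove it. Discretion with no upper limit leaves the worst permitted case at a full visit interval. Section 13.2.9 is headed as covering other abnormalities; its reach to the liver rows is arguable, and the liver has its own section, which says to interrupt. Low expected frequency limits how many boys are affected, and not what the rule permits for one of them.

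A reader might infer that the ALT/CK signal is in the same position. The documents do not support that. Drug continues by design in that row, and Section 13.2.5 already asks for more frequent testing. It is true that Section 6.3.2 words this only as "the recommended diagnostic workup may include more" frequent monitoring, and that Table 2 puts work-up after confirmation. A late work-up could therefore postpone a discretionary stop, but that is not exposure created by the rule.

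**Conclusion.** The point holds, at minor severity. Footnote a permits, without requiring, a wait of 70 to 98 days for the repeat test behind the stop-after-confirming rule, with 70 to 90 days of dosing in that time. For Grade 2 bilirubin and GGT this sits poorly with Section 13.2.5.

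The 70 to 90 days rest on stated visit windows, supply and full compliance. The saving of 56 to 83 days also assumes a 7-day limit, a report lag of 0 to 7 days, and an interval that ends before Week 144. The documents do not say how often Grade 2 values occur.

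Three further readings go too far:
- That confirming before stopping is itself the fault. Section 13.2.3 accepts it; only the length of the wait is at issue.
- That liver values deserve a limit and renal values do not. The same wait covers the renal and electrolyte rows, and nothing in the documents ranks liver risk higher.
- That the wait has caused harm. Nothing in the documents shows this.

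**What to change.** Replace footnote a in Protocol Table 2 with wording such as:

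> Values in the stop-after-confirming column, at minimum Grade 2 bilirubin and Grade 2 GGT, must be confirmed by an unscheduled repeat sample within a sponsor-set limit (for example 7 days) of the result being reported, without waiting for the next scheduled visit.

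The new text should not restate next-visit confirmation as acceptable for the renal and potassium rows. Ideally the limit covers the whole column. For ALT/CK, a cross-reference to the increased monitoring in Section 13.2.5 is enough. The copy in SAP Table 2 changes only for consistency.

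The cost is one footnote in an amendment and an occasional between-visit sample, which the present footnote already permits: one 5 mL serum tube for biochemistry (Protocol Table 4), or a urine sample for the urine rows. The real burden is travel, since Section 13.1.7 notes that many families live far from their site. The benefit is limited to patients still being dosed.
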